Objectives:	To demonstrate that the safety and performance profile of the Neurotech Vital Compact (delivering electrical stimulation through external electrodes) is equivalent to the itouch Sure Pelvic Floor Exerciser (delivering electrical stimulation through an internal vaginal probe).
Primary Endpoint:	The primary endpoint is defined as the proportion of subjects considered to have achieved at least a 50% reduction in pad weight following a provocative pad weight test at 12 weeks compared to baseline.
Key Secondary Endpoints:	
The following key secondary endpoints will each be analysed, for superiority, at a 5% two-sided significance level with a view to support labelling. In order to control the type I error rate the endpoints will be analysed in the following hierarchy (Statistical Plan will supply further details). If any endpoint in the sequence fails to show a statistically significant difference then the inference is that there is insufficient evidence both for that endpoint and the subsequent endpoints in the hierarchy.
 
1. Between group comparison of mean change, with respect to baseline, in urine leakage in a provocative pad weight test at Week 12;2. Within Neurotech Vital Compact group estimate of mean change, with respect to baseline, in urine leakage in a provocative pad weight test at Week 12;3. Between group comparison of mean change, with respect to baseline, in urine leakage in the 24-hour pad weight test at Week 12;4. Within Neurotech Vital Compact group estimate of mean change, with respect to baseline, in urine leakage in the 24-hour pad weight test at Week 12;5. Between group comparison of mean change, with respect to baseline, in the number of incontinence

	
episodes/day recorded using a 7-day voiding diary at Week 12;
 
6. Within Neurotech Vital Compact group estimate of mean change, with respect to baseline, in the number of incontinence episodes/day recorded using a 7-day voiding diary at Week 12;7. Between group comparison of the mean improvement, with respect to baseline, in Incontinence Quality of Life Questionnaire (I-QOL) score at Week 12;8. Within Neurotech Vital Compact group estimate of mean improvement, with respect to baseline, in Incontinence Quality of Life Questionnaire (I-QOL) score at Week 12;9. Between group comparison of mean change, with respect to baseline, in the number of pads used/day recorded using a 7-day voiding diary at Week 12;10. Within Neurotech Vital Compact group estimate of mean change, with respect to baseline, in the number of pads used/day recorded using a 7-day voiding diary at Week 12;11. Between group comparison of the proportion of subjects achieving dryness at Week 12 (<1g on the provocative pad weight test).
Other Secondary Endpoints:	
Other secondary endpoints that will be evaluated at 4 weeks and 26 weeks are as follows:
 
• Proportion of subjects considered to have achieved significant improvement, defined as a greater than 50% reduction in pad weight, from baseline on the provocative pad weight test.• Urine leakage on the provocative pad weight test (following standardized bladder-filling protocol).• Urine leakage experienced by the subject at home in the 24-hour pad weight test;• Incontinence episodes/day recorded using a 7-day voiding diary;• Proportion of subjects achieving dryness (<1g on the provocative pad weight test)• Improvement in quality of life assessed using the Incontinence Quality of Life Questionnaire (I-QOL);• Number of pads/day recorded using a 7-day voiding diary;• Dryness, defined as a pad weight of less than 1.3g on the 24-hour pad weight test (including an evaluation at 12 weeks);• Proportion of subjects considered to have achieved

	
significant improvement, defined as a greater than 50% reduction in pad weight, from baseline on the 24-hour pad weight test (including an evaluation at 12 weeks).
 
Other data that will be evaluated are as follows:
 
• Proportion of subjects achieving dryness at Week 12 in each group (<1g on the provocative pad weight test).• Within Neurotech Vital Compact group estimate of mean change, with respect to baseline, in sexual function as measured by the Pelvic Organ Prolapse/Urinary Incontinence Sexual Questionnaire (PISQ-IR) at Week 12;• Between group comparison of mean change, with respect to baseline, in sexual function as measured by the Pelvic Organ Prolapse/Urinary Incontinence Sexual Questionnaire (PISQ-IR) at Week 12;• Within Neurotech Vital Compact group estimate of patient response to the Patient Global Impression of Improvement (PGI-I) at Week 12.• Between group comparison of patient response to the Patient Global Impression of Improvement (PGI-I) at Week 12;• Safety in relation to adverse events and device deficiencies reported;• Evaluation of reduction in urine leakage on the provocative pad weight test in relation to the mean intensity of the stimulation delivered during the 12-week treatment programme;• Evaluation of the reduction in urine leakage on the provocative pad weight test at Week 12 in relation to the BMI category (underweight/normal/overweight/obese) of the subjects;• Evaluation of the reduction in urine leakage on the provocative pad weight test at Week 12 in relation to the baseline severity of stress urinary incontinence of the subjects;• Device compliance of the Neurotech Vital Compact device with the treatment protocol during the 12-week treatment programme;• Device compliance of the itouch Sure Pelvic Floor Exerciser with the treatment protocol during the 12-week treatment programme;
Indication:	Stress urinary incontinence defined as 'complaint of involuntary leakage on effort or exertion, or on sneezing'

	and coughing' (International Continence Society).
Inclusion Criteria:	
 Subjects who are female and at least 18 years of age, and not more than 65 years of age. Subjects who have signed an informed consent form prior to any study related activity. Subjects who have previously tried and failed to improve their condition using Kegel exercises. Subjects who have been clinically diagnosed with stress urinary incontinence and demonstrate a greater than or equal to 3g urine leakage and a less than or equal to 90g urine leakage ($\geq 3g$ and $\leq 90g$) following a bladder-filling protocol and then a standardised stress test (provocative pad weight test) at the baseline assessment. Subjects who score 9 or less (≤ 9) out of 18 for the Urge Incontinence Questions and are confirmed as having predominant stress urinary incontinence on the Medical, Epidemiologic and Social Aspects of Aging Urinary Incontinence (MESA) Questionnaire completed at the screening assessment. Subjects with a Body Mass Index of $\leq 35 \text{ kg/m}^2$. Subjects of child-bearing potential who are using a highly effective contraceptive method (established use of oral, injected, implanted hormonal method of contraception or barrier method of contraception with spermicide). Subjects who are willing not to seek any other treatment for stress incontinence during the study period. Subjects who are able to give voluntary, written informed consent to participate in this study and from whom consent has been obtained. Subjects who are able to understand this study and are willing to complete all the study assessments.
Exclusion Criteria:	
 Subjects who have an existing medical condition that would compromise their participation in the study, e.g. reduced sensory perception in the contact area of the stimulation electrodes; scars or vaginal tissue wounds, lesions or inflamed/infected areas in the contact area of the stimulation electrodes; vaginal bleeding between menstrual periods; uncontrolled diabetes. Subjects who have a physical condition that would make them unable to perform the study procedures, e.g. pelvic or hip surgery within the past 6 weeks. Subjects who have been diagnosed with Chronic Obstructive Pulmonary Disease (COPD). Subjects with a history of an underlying neurological condition, e.g. Multiple Sclerosis, Parkinson's disease,

	
epilepsy.
 
• Subjects with any bladder abnormality that would affect the urinary flow through the lower urinary tract including symptoms of a urinary tract infection, abnormal bladder capacity (e.g., >300 cc), post void residual volume >200 cc, spastic bladder, vesico-ureteral reflux or bladder stones.• Subjects with a blood clotting disorder or who are taking anti-coagulant medications.• Subjects who have previously had any urogynaecological related surgery that would affect the pelvic floor muscles or urinary flow through the urethra (excluding hysterectomy).• Subjects who have previously had pelvic floor radiation.• Subjects who have previously been treated for stress incontinence with injectable bulking agents and/or vaginal probes within the past 6 months.• Subjects with a clinical diagnosis of prolapse greater than Stage 2.• Subjects who are pregnant or could be pregnant.• Subjects who are less than 6 months post-partum or who are lactating.• Subjects who have any conductive intra-uterine devices or metal implants in the pelvic area, including hip and lumbar spine.• Subjects with pelvic pain or fibromyalgia or paravaginal defect.• Subjects with an active implanted medical device (e.g. pacemaker, insulin pump) or conditions that may be adversely affected by electrical stimulation (e.g. cardiac arrhythmias).• Subjects with a current or active history of pelvic cancer and/or subjects with a life expectancy of less than 12 months.• Subjects who are currently involved in any injury litigation claims.• Subjects who have participated in a clinical study in the last 3 months or any previous clinical study with Bio-Medical Research Ltd.• Subjects who have been committed to an institution by virtue of an order issued either by the courts or by an authority.
Study Sites:	Approximately 12 USA sites
Number of subjects planned:	Approximately 180 subjects (90 subjects per group).
Target population:	The patient population will be females with stress incontinence.

Study duration:	Subjects included in the clinical study will be evaluated at screening, on enrolment into the study (baseline) and during the 12-week treatment programme at 4 and 12 weeks. Telephone calls will be made at 1 week to check on the patient's progress during their initial use of the device. Subjects will also be evaluated at 26 weeks following the commencement of the treatment. The recruitment period is estimated as 12 months with an anticipated study duration of 28 months.
Study device/procedure:	Neurotech Vital Compact device is CE approved as a Class IIa Device in Europe, in line with Medical Device Directive 93/42/EC as amended by 2007/47/EC. FDA has determined that Neurotech Vital Compact is a Non-Significant Risk device. The study is therefore classed as a Non-Significant Risk Device Study and accordingly it will be conducted in accordance with the abbreviated Investigational Device Exemption (IDE) requirements set forth in 21 CFR 812.2(b) in the USA.
Comparator device/procedure:	The itouch Sure Pelvic Floor Exerciser (manufactured by TensCare Ltd., UK) is cleared by the FDA through the 510 (k) premarket notification process (K103698) in the USA.
Device treatment program:	Subjects who are considered eligible to participate in the clinical study and give consent will be randomised to complete either a 12-week treatment programme with the Neurotech Vital Compact or a 12-week treatment programme with the itouch Sure Pelvic Floor Exerciser. The 12-week treatment programme will be completed by the subjects at home with the device in accordance with the device Instructions for Use. The Neurotech Vital Compact is used for five days each week (each daily session of 30 minutes) with two rest days taken within a 7 day week period, for the 12-week period. The itouch Sure Pelvic Floor Exerciser is used once per day (each daily session of 20 minutes) during the 12-week period.
Performance assessments:	Performance will be assessed by: provocative pad weight test following a standardized bladder-filling protocol verified by ultrasound bladder scanning; 24-hour pad weight test; Incontinence Quality of Life Questionnaire (I-QOL); incontinence episodes/day and number of pads used/day from 7-day voiding diary; and assessment of 'dryness' and 'significantly improved'.
Safety assessments:	Safety will be assessed in terms of severity, frequency and seriousness of any adverse events or adverse device effects.
Concomitant Medication and/or	
 Subjects may use any medication that has an effect upon urinary output function if a) the medication has

Treatments:	
been used for at least 4 weeks prior to study enrolment and b) the medication regimen is not changed during the 12-week device treatment program
 
 • No device re-treatment will be allowed during the subject's participation in the study.
Single-Blind Status:	
The study is considered single-blind as the subjects will be randomised to the Neurotech Vital Compact device or the itouch Sure Pelvic Floor Exerciser (ratio 1:1). Since the two devices will be described in detail in the patient information sheet, the patients will know which device they have been randomised to i.e. the Neurotech Vital Compact device delivers electrical stimulation through external electrodes and the itouch Sure Pelvic Floor Exerciser delivers electrical stimulation through an internal vaginal probe. It is not believed this will introduce any bias since patients would not have an expectation that either device is better than the other.
 
The site personnel who allocate the devices, perform the device training at baseline and monitor the device compliance at the follow-up visits will not be blinded, but the personnel who perform the follow-up assessments will be blinded. The statistical analysis will be blinded until data base lock
 
Verification to ensure that this blinding is maintained will be assessed at the monitoring visits.

STUDY ASSESSMENTS Visit 1: Screening	
 • Demographic data including height and weight. • Medical history including details of stress urinary incontinence, previous bladder/kidney infections and any current/previous urological treatments. • Physical examination including a detailed urological examination to assess urinary symptoms and symptoms of bowel function, sexual function and pelvic organ prolapse. • Details of all medication (over-the-counter and prescription) and dietary/herbal supplements in the previous 6 months. • Urine pregnancy test to confirm subject is not pregnant (women of child-bearing potential only). • Complete the Medical, Epidemiologic and Social Aspects of Aging Urinary Incontinence (MESA) Questionnaire (patient quality of life questionnaire). • Complete a standardized stress test to evaluate amount of urine lost following a standardized bladder-filling protocol verified by ultrasound (provocative pad weight test). The data from this test will not be used for

	
analysis purposes, it is only to allow patients to practise the stress test. Further details are provided in Appendix I.
 
• Record any cough or cold symptoms.• Record any adverse events. 
Prior to leaving the clinic, subjects will also be provided with the following:
 
• A 7-day voiding diary to complete prior to Visit 2 (baseline) appointment.• Pre-weighed incontinence pads in a sealed bag to complete the 24-hour pad collection for three days prior to the Visit 2 (baseline) appointment. Any subjects menstruating during this time will also be asked to record this on the voiding diary. Any subjects who have sexual intercourse during this time will be asked to expel any fluid post-intercourse and will be asked also to record this on the voiding diary.
Assessments Visit 2: Baseline	
• Complete the Incontinence Quality of Life Questionnaire (I-QOL) (patient quality of life questionnaire).• Complete the Pelvic Organ Prolapse/Urinary Incontinence Sexual Questionnaire (PISQ-IR)• Complete a standardized stress test to evaluate amount of urine lost following a standardized bladder-filling protocol verified by ultrasound bladder scanning (provocative pad weight test). This is used to determine eligibility to participate. Further details are provided in Appendix I.• Number of incontinence episodes/day from 7-day voiding diary.• Number of pads used/day from 7-day voiding diary.• Mean weight of urine lost during three consecutive 24-hour periods at home (difference in post- and pre-weight incontinence pads) (24-hour pad weight test).• Record any medication use since the last visit.• Record any cough or cold symptoms since the last visit.• Record any adverse events since the last visit.• Subject training on use of device and complete one session in clinic 
Prior to leaving the clinic, subjects will also be provided with the following:
 
• A 7-day voiding diary to complete prior to Visit 3 appointment.• Pre-weighed incontinence pads in a sealed bag to complete the 24-hour pad collection for three days prior to the Visit 3 appointment. Any subjects menstruating during this time will also be asked to record this on the

	
voiding diary. Any subjects who have sexual intercourse during this time will be asked to expel any fluid post-intercourse and will be asked also to record this on the voiding diary.

Telephone call: 1 week	
 Telephone call to check the patient is happy with the treatment set up and using the device as per the instructions and to assess if there any adverse events and/or changes to medication.
Assessments Visit 3: 4 weeks Assessments Visit 4: 12 week Assessments Visit 5: 26 week	
 Urine pregnancy test to confirm subject is not pregnant (pre-menopausal subjects only) (Week 4 assessment only). Complete the Incontinence Quality of Life Questionnaire (I-QOL) (patient quality of life questionnaire). Complete Pelvic Organ Prolapse/Urinary Incontinence Sexual Questionnaire (PISQ-IR) (Week 12 assessment only). Complete Patient Global Impression of Improvement (PGI-I) (Week 12 assessment only). Complete a standardized provocative stress test to evaluate amount of urine lost following a standardized bladder-filling protocol (provocative pad weight test) Number of incontinence episodes/day from 7-day voiding diary. Number of pads used/day from 7-day voiding diary. Mean weight of urine lost during a three day 24-hour period at home (difference in post- and pre-weight incontinence pads) (24-hour pad weight test). Record any medication use since the last visit. Record any cough or cold symptoms since the last visit. Record any adverse events since the last visit. Data from the device will be downloaded to determine stimulation intensity and duration of treatment were completed according to the planned treatment programme (Week 4 and 12 assessment only and completed by unblinded study personnel). 
At Visit 4, subjects will also be provided with training and an instruction flyer for pelvic floor exercises (Kegel exercises). Participants will be advised to perform Kegel exercises from 12 weeks to the 26 weeks follow-up.
 
Prior to leaving the clinic at Visit 3 and 4, subjects will also be provided with the following:
 
 A 7-day voiding diary to complete prior to next appointment. Pre-weighed incontinence pads in a sealed bag to complete the 24-hour pad collection for three days prior to the next appointment. Any subjects menstruating

	
during this time will also be asked to record this on the voiding diary. Any subjects who have sexual intercourse during this time will be asked to expel any fluid post-intercourse and will be asked also to record this on the voiding diary.

--	---------------------------------------------------------------------------------------------------------------------------------------------------------------------------------------------------------------------------------------------------------

Personnel Involved in the Study

Role	Name

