2.3 Rationale of Neurotech Vital Compact Device

The research evidence supporting the use of electrical stimulation (ES) in pelvic floor neuromuscular rehabilitation for stress urinary incontinence (SUI) is somewhat equivocal. While some studies (Castro, 2008; Sand, 1995) have shown a beneficial effect of ES that is comparable to other conservative interventions, there are other studies which have failed to show a clear benefit (Bo, 1999). There has been a lack of homogeneity in the study designs and most especially in the equipment used. Most studies have used one or other of the commercially available trans-vaginal ES systems and little information has been provided as to the effectiveness of the particular system used in activating the target muscle group. A further difficulty with transvaginal ES is that some patients object to using the intra-vaginal probe electrodes. A novel form of ES for pelvic floor stimulation has been developed which utilises an array of external electrodes and this is believed, based on observation using pelvic floor (PF) ultrasonography, to deliver much greater levels of PF muscle activation than the transvaginal approach.

Thus in this study we will be using the Neurotech Vital Compact device to deliver neuromuscular electrical stimulation (NMES) to the pelvic floor muscles via an arrangement of external electrodes optimally positioned to successfully stimulate these muscles and held in place by a garment to facilitate good skin contact and repeatability of positioning. The

Neurotech Vital Compact device is the fourth generation of the device which has been developed using the same technology as the UCD RS device (first generation device) and Inko RS device (second generation device).

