2.5 Rationale of a Single-Blind Study Design

The study is considered single-blind as the subjects will be randomised to either the Neurotech Vital Compact device or the itouch Sure Pelvic Floor Exerciser. Since the two devices will be described in detail in the patient information sheet, the patients will know to which device they have been randomised, i.e. the Neurotech Vital Compact device delivers electrical stimulation through external electrodes and the itouch Sure Pelvic Floor Exerciser delivers electrical stimulation through an internal vaginal probe. This should not introduce any bias since patients would not have an expectation that the new device (Neurotech Vital Compact device) is better than the existing active control device (itouch Sure Pelvic Floor Exerciser).

The site personnel who allocate the devices, perform the device training at baseline and monitor the device compliance at the follow-up visits will not be blinded, but the personnel who perform the follow-up assessments will be blinded.

Verification to ensure that this blinding is maintained will be assessed at the monitoring visits.

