2.7 Risk/Benefit Rationale

NMES is a safe treatment option for stress urinary incontinence. Once patients have been trained in the use of the device and application of the electrodes and associated garments, self-treatment is continued at home for up to 12 weeks without the need for prolonged interim hospital visits as part of routine care. The Neurotech Vital Compact device can be used with external electrode placement which is more acceptable for patients than the use of internal (vaginal or anal) electrodes or other internal devices.

Alternative non NMES treatment options such as Kegel pelvic floor exercises are not successful for many patients for a variety of reasons and may require regular motivational visits during the

training period. Pharmaceutical options for stress urinary incontinence are very limited and are not suitable for all patients.

Ultimately, surgical intervention provides relief for many patients but is obviously fraught with inherent surgical and anaesthetic risks not seen in less invasive therapies, in addition to hospital costs.

Therefore, there is a safety and cost benefit for the use of an external NMES device over alternative treatment options including surgery.

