6.2 Inclusion Criteria

1. Subjects who are female and at least 18 years of age, and not more than 65 years of age.
2. Subjects who have signed the informed consent form prior to any study related activity.
3. Subjects who have previously tried and failed to improve their condition using Kegel exercises.
4. Subjects who have been clinically diagnosed with stress urinary incontinence and demonstrate a greater than or equal to 3g urine leakage and a less than or equal to 90g urine leakage ($\geq 3g$ and $\leq 90g$) following a bladder-filling protocol and then a standardised stress test (provocative pad weight test) at the baseline assessment.
5. Subjects who score 9 or less (≤ 9) out of 18 for the Urge Incontinence Questions and are confirmed as having predominant stress urinary incontinence on the Medical, Epidemiologic and Social Aspects of Aging Urinary Incontinence (MESA) Questionnaire completed at the screening assessment.
6. Subjects with a Body Mass Index of $\leq 35 \text{ kg/m}^2$.
7. Subjects of child-bearing potential who are using a highly effective contraceptive method (established use of oral, injected, implanted hormonal method of contraception or barrier method of contraception with spermicide).
8. Subjects who are willing not to seek any other treatment for stress incontinence during the study period.
9. Subjects who are able to give voluntary, written informed consent to participate in this study and from whom consent has been obtained.
10. Subjects who are able to understand this study and are willing to complete all the study assessments.

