2 ANALYSIS

2.1 ANALYSIS POPULATIONS

The primary analysis population will be the intent to treat (ITT) population. This will include all randomized subjects. Subjects will be summarized according to their randomized assignment. If there are randomized subjects who do not use the device at least once, a modified ITT (mITT) population will be defined to exclude such subjects and this population will be used in place of ITT.

A per-protocol (PP) population will also be evaluated for the primary endpoint. This population will consist of subjects who:

- Signed informed consent
- Met inclusion/exclusion criteria
- Were treated per randomized assignment
- Had 12 week outcome data available
- Met study compliance criteria
- No significant protocol deviations

Prior to locking the database, the PP criteria will be reviewed, additional criteria will be added if needed, and a listing of PP violations will be generated. The Sponsor/CRO will review this list and determine exclusions from this population. The final list of PP criteria and exclusions will be documented prior to unblinding.

The Safety population will include all randomized subjects who used the device at least once. Subjects will be summarized according to the actual device used, rather than the randomized assignment.

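### Eligibility asks for willingness to complete assessments but not to use either allocated device, so refusal after allocation may fall mainly on the vaginal-probe arm

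*Protocol*

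**What the plan says.** Criterion 10 in Protocol 6.2, repeated in the synopsis, reads "Subjects who are able to understand this study and are willing to complete all the study assessments". The only other criterion worded as willingness is criterion 8, about not seeking other treatment. No inclusion or exclusion criterion mentions willingness to use the allocated device.

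The protocol itself expects the two routes to differ in acceptability. Section 2.3 states: "A further difficulty with transvaginal ES is that some patients object to using the intra-vaginal probe electrodes". Section 2.7 describes "external electrode placement which is more acceptable for patients than the use of internal (vaginal or anal) electrodes".

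The order of events is set out in 8.8 and 8.10.1. Baseline assessments and eligibility come first, then the envelope, then device training with a first session in clinic. Women know which device they have been given (7.5). Those withdrawn after the baseline assessments are not replaced (6.4).

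On analysis, SAP 2.1 deals with randomised women who never use their device as follows: "a modified ITT (mITT) population will be defined to exclude such subjects and this population will be used in place of ITT". For women who start treatment and then stop, Protocol 8.11.1 asks them back for an early termination visit, and SAP 1.6.2 records that visit as Week 12. Multiple imputation applies only where the Week 12 assessment is not completed (Protocol 10.3.4, SAP 2.3.2.1).

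**The concern.** A woman who would use the external garment but not a vaginal probe meets every listed criterion. If she is allocated Vital, her reluctance never shows. If she is allocated itouch, she may refuse at the first session, and the mITT rule then takes her out of the primary comparison. Her counterpart in the Vital arm stays in. The two analysed groups would then no longer be the groups that randomisation made.

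The protocol's case for tolerating unblinded subjects does not deal with this. It argues that "patients would not have an expectation that either device is better than the other". That concerns expected benefit, not whether a woman will accept the route of delivery.

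At stake is a non-inferiority conclusion judged against a 5-point margin, where removing a modest number of women from one arm can move the estimate by a similar amount.

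**Working it through.** **Inputs from the documents** (Protocol 10.2, SAP 1.4): response 52% on itouch and 71% on Vital, margin 5 points, one-sided 0.025, 90% power, 87 per group raised to 90.

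**Assumed, because neither document gives a figure:** the fraction *q* of itouch women who never use the device (5% or 10%; 10% of 90 is 9 women), and the response rate *r* those women would have had on itouch.

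**1. The plan's own sample size.** With unpooled variance, n = (0.71×0.29 + 0.52×0.48) × (1.960 + 1.282)² / (0.71 − 0.52 + 0.05)² = 83.1, so 84 per group. With a pooled variance under the null, or the Farrington-Manning variance, it is 85.1, so 86. Unpooled power at 87 per group is 91.3%. The stated 87 is close to these and is not in dispute.

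**2. Effect on power.** Power = Φ[(0.71 − 0.52 + 0.05)/SE − 1.960], with SE = √(0.71×0.29/90 + 0.52×0.48/n_itouch) and response rates unchanged.

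| itouch women dropped | n itouch | Power |
|---|---|---|
| 0% | 90 | 92.1% |
| 5% | 85.5 | 91.4% |
| 10% | 81 | 90.6% |
| 20% | 72 | 88.6% |

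Lost numbers are not the problem.

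**3. Effect on the estimate under the mITT rule.** Hold the full itouch arm at 52% and leave the Vital arm untouched. The retained itouch rate is (0.52 − q·r)/(1 − q). The shift in the Vital minus itouch difference is 0.52 minus that rate.

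| q | r | Retained itouch rate | Shift in difference |
|---|---|---|---|
| 5% | 0% | 0.52/0.95 = 54.7% | −2.7 points |
| 10% | 0% | 0.52/0.90 = 57.8% | −5.8 points |
| 5% | 52% | 52.0% | 0 |
| 10% | 52% | 52.0% | 0 |
| 5% | 71% | (0.52 − 0.0355)/0.95 = 51.0% | +1.0 point |
| 10% | 71% | (0.52 − 0.071)/0.90 = 49.9% | +2.1 points |

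Removing likely non-responders raises the itouch rate and works against Vital. Removing likely responders works in its favour. If refusers resemble everyone else, nothing moves.

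**4. Who is actually removed.** The first session is in clinic straight after randomisation, and SAP 3.7 has it entered in the use record. On a plain reading, only women who refuse by that point and never return to the device are never-users. A woman who completes one session and stops at home stays in the analysis, with an early termination visit if she attends and an imputed value if she does not.

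**The case against.** The strongest reply is that consent already does this work. Criterion 9 requires "Subjects who are able to give voluntary, written informed consent to participate in this study and from whom consent has been obtained", criterion 2 requires a signed form, and "the two devices will be described in detail in the patient information sheet". Subjects get time to decide (8.3), and 8.6 allows 2 to 4 weeks for discussion, consent and evaluation. A woman who firmly objects to a probe can decline, or can leave before baseline is complete and be replaced. Women for whom a probe is medically unsuitable are largely covered by the exclusions for vaginal lesions or infection and for pelvic pain.

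Much of this stands. Consent is an eligibility criterion and will screen out some objectors. The sample consent form was not available for review, so it may already ask for acceptance of either device. What remains is that agreeing to enter a randomised study, with freedom to withdraw, is not a recorded statement that the woman will use whichever device she draws.

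Three stronger readings are tempting, and the documents do not support them:

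- *Loss from the itouch arm only.* No refusal or dropout rate is given for either arm. Vital has burdens of its own: a pilot subject had an allergic skin reaction to the electrodes (2.1), electrode sensitivity is an anticipated event (9.2), and standing is the recommended position for the session (Appendix XI). Withdrawal for failed training applies to both devices (8.10.1). Mainly itouch is plausible; only itouch is not shown.
- *Early stoppers are simply imputed.* They are asked back and recorded as Week 12, and are imputed only if they do not return. The tipping-point analysis in SAP 2.3.2.2 runs through every outcome combination for missing values, although where the mITT replaces the ITT it would not appear to reach never-users.
- *Refusers depress the itouch rate and so flatter Vital.* That requires counting refusers as failures, which neither document plans.

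**Conclusion.** The point holds as a gap in the eligibility text. Willingness to use either device is not asked for, the protocol itself reports objection to one of the two routes, and the SAP turns never using the device into exclusion from the primary analysis.

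Its size cannot be fixed from the documents. At an assumed 5% to 10% of itouch women dropped, and no matching loss from Vital, the difference could shift anywhere from −5.8 to +2.1 points, depending on how those women would have responded. The lower end exceeds the 5-point margin in size, but it requires 10% loss and that none of those women would have responded. It also works against the sponsor's device. Power stays above 90% across that range.

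This is an inexpensive improvement to make, not evidence that the planned comparison is biased in a known direction.

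**What to change.** Extend criterion 10 in 6.2, and the matching synopsis entry, so that it also requires the subject to be *willing to use either study device, including a vaginal probe, as allocated*. Record her answer on the eligibility CRF at Visit 2, before the randomisation envelope is opened, so that an objection surfaces while she can still be replaced.

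The cost is one clause in two places and one CRF item. A few women will not be enrolled, and the population becomes slightly narrower, limited to those who would accept either route. A woman can still agree and then refuse. The clause should reduce the number of never-users, but it does not change how SAP 2.1 treats those who remain.
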